Subjects participating in the proposed study will receive standard treatment that meets (or exceeds) the quality of treatment available in the community. Repetitive TMS (rTMS) is currently approved for the treatment of depression; although it is not approved for the management of post-stroke aphasia, many studies support its use in this clinical setting. However, patients/legal guardians will be told that rTMS is not currently FDA approved for this indication or population in which it is being used. The proposed study does not require an IND submission, since it meets the following requirements of the Center for Drug Evaluation and Research: (1) it is not intended to be reported to FDA in support of a new indication for use or to support any other significant change in the labeling for the drug; (2) it is not intended to support a significant change in the advertising for the product; (3) it does not involve a route of administration or dosage level, use in a subject population, or other factor that significantly increases the risks (or decreases the acceptability of the risks) associated with the use of the drug product; (4) it is conducted in compliance with the requirements for UAB IRB review and informed consent; (5) it is conducted in compliance with the requirements concerning the promotion and sale of drugs/treatments; and (6) it does not invoke 21 CFR 50.24 (exception from informed consent requirements for emergency research).

Finally, the trial will be registered at www.clinicaltrials.gov.

DSMB – manual of operation

1. Introduction
2. Primary Responsibilities of the DSMB
3. Membership of the DSMB
 - a. Members
 - b. Conflicts of Interest

4. Timing and Purpose of the DSMB Meetings
 - a. Organizational Meeting
 - b. Early Safety/Trial Integrity Reviews
 - c. Formal Interim Efficacy Analysis
5. Procedures to Ensure Confidentiality
6. Communication
 - a. Closed Sessions
 - b. Open Session
 - c. Open and Closed Reports
 - d. Minutes of the DSMB Meeting
 - e. Recommendations to the PI
7. Statistical Monitoring Guidelines
8. Content of the DSMB's Open and Closed Reports

1. Introduction

This Charter is for the Data and Safety Monitoring Board (DSMB) for protocol "Post-stroke aphasia and rTMS treatment (PART) study".

The Charter will define the primary responsibilities of the DSMB, its membership, and the purpose and timing of its meetings. The Charter will also provide the procedures for ensuring confidentiality and proper communication, the statistical monitoring guidelines to be implemented by the DSMB, and an outline of the content of the Open and Closed Reports that will be provided to the DSMB.

2. Primary Responsibilities of the DSMB

The DSMB will be responsible for safeguarding the interests of trial participants, and assessing the safety and efficacy of the interventions during the trial (rTMS and or combined rTMS and CIAT). This responsibility will be exercised by providing recommendations about stopping or continuing the trial. To contribute to enhancing the integrity of the trial, the DSMB may also formulate recommendations relating to the selection/recruitment/retention of participants, their management, improving adherence to protocol-specified regimens and retention of participants, and the procedures for data management and quality control.

The DSMB will be advisory to the principal sponsor-investigator [name], PhD. The PI will be responsible for promptly reviewing the DSMB recommendations, to decide whether to continue or terminate the trial, and to determine whether amendments to the protocol or changes in study conduct are required. *If an investigator does not agree with the DSMB recommendations then a memo justifying the reasons for not complying with the recommendations must accompany the minutes.*

3. Membership - a. Members

The DSMB will consist of at least 4 independent clinicians and biostatisticians that, collectively, have experience in the management of patients with strokes associated with aphasia and in the conduct and monitoring of randomized clinical trials. A quorum will require at least 3 members, including the chair.

DSMB Chair: [name]
CAHS Rehabilitation Sciences
[contact]
[name]

Biostatistician: [name]
Department of Public Health
[contact]
[name]

Other DSMB Members:

[name]
Department of Neurology
[contact]
[name]

[name]
Department of Neurology
[contact]
[name]

Conflicts of Interest

The DSMB membership has been restricted to individuals free of apparent significant conflicts of interest. The source of these conflicts may be financial, scientific or regulatory in nature. Thus, study investigators are not members of the DSMB.

The DSMB members will disclose conflicts of interest to fellow members. Any DSMB member who has or develops a significant conflict of interest should resign from the DSMB.

DSMB membership is for the duration of the clinical trial. If any members leave the DSMB during the course of the trial, the PI will promptly appoint their replacement.

4. Timing and Purpose of the DSMB Meetings

The first meeting of the DSMB will occur 3 months after study initiation (official date of the IRB approval). The reviews will be done in person or via teleconference. The study team is responsible for coordinating the venue for the DSMB meetings, i.e. establishing the meeting date and time, reserving the conference room, arranging for teleconference equipment. The purpose of the DSMB meetings is to review the conduct of the trial to date and assess safety and efficacy of the study intervention (rTMS). The DSMB will review SAEs and determine whether the study should be prematurely discontinued.

Ad hoc meetings may be scheduled as needed.

5. Confidentiality

A format for Open and Closed Sessions should be implemented. The intent of this format is to enable the DSMB to preserve confidentiality of the comparative efficacy results while at the same time providing opportunities for interaction between the DSMB and study team. DSMB personnel will not have access to unblinded data; group comparisons will be provided by study statistician ([name]).

The study arm assignment for individual participants may be disclosed on a case-by-case basis. Request to unblind must be provided by DSMB Chair in writing. The DSMB will have responsibility for assessing and making recommendations to correct any possible abuses of the disclosure privilege.

6. Communication

Open Session

The Open Session provides the DSMB an opportunity to query the study team about issues that have arisen during the review of the data.

Closed Session

Sessions involving only DSMB membership and the independent biostatistician who generated the Closed Reports will be held to allow discussion of confidential data from the clinical trial, including information about the relative efficacy and safety of interventions. The DSMB will develop a consensus on its list of recommendations, including whether the trial should continue.

DSMB Meeting Minutes

Depending on the issues and protocol, a DSMB meeting may have both Open and Closed meeting minutes. Meeting minutes should be distributed as soon as possible after the DSMB meeting. IRB needs to be included on the distribution list. At the time of IRB annual renewal, DSMB minutes will be required, if not already provided.

7. Statistical Monitoring Guidelines

Study will not be terminated if there is evidence that one of the treatment conditions has better side effects profile or efficacy unless statistically significant difference in favor of one of the treatment arms is observed in at least 50% of the variables.

8. Content of Reports for the DSMB

- Study number and title. Brief summary of the study design.
- Protocol amendments
- Status of accrual. If accrual is slower than expected, a plan for increasing enrollment.
- Status of participating sites (for Multi-Center trials)
- Compliance

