Post-Stroke Aphasia and RTMS Treatment (PART)

Study Protocol & Statistical Analysis Plan

NCT01512264

April 1, 2019

[name], PHD, Principal Investigator

University of Alabama at Birmingham

Birmingham, AL 35294

**POST-STROKE APHASIA AND RTMS TREATMENT (PART) STUDY
NIH R01 HD068488**

PI: [name], PHD

Co-I'S:

UC: [name], PHD

**UAB: [name], PHD (BLINDED TO TREATMENT
ASSIGNMENT)
[name] (BLINDED TO TREATMENT ASSIGNMENT)**

**RTMS TREATMENT TEAM
[name]
[name], PHD
[name], PHD
[name]**

**CIAT TREATMENT TEAM
[name]
[name], SLP
[name], SLP**

OTHER STUDY PERSONNEL:

[name], BS (BLINDED TO TREATMENT ASSIGNMENT)

PART Study Protocol

This study will test two hypotheses:

Hypothesis 1: Navigated excitatory rTMS (nerTMS) will improve language outcomes when applied to the peri-stroke language areas identified by fMRI in patients with chronic (>1 year) aphasia caused by a left middle cerebral artery (LMCA) stroke when compared to sham treatment (ST); synergistic effect is expected in subjects treated with a combination of nerTMS and CIAT. Treatment response, as measured with qualitative and quantitative aphasia testing (AT), will depend on treatment duration.

Hypothesis 2: Improved language performance will be associated with increased left-lateralization of language networks following nerTMS as assessed by fMRI. This left-hemispheric shift of language processing will correlate with behavioral response to nerTMS, representing evidence of clinical efficacy; the degree of the post-intervention recovery will correlate with the degree of the left-sided language shift.

The following specific aims were designed to test these hypotheses:

Aim 1 (treatment): To determine the comparative efficacy and optimal dosing of nerTMS on aphasia recovery using a randomized, double-blind, sham-controlled study design. Subjects (15/group) will be randomly assigned to 4 treatment groups: (a) 3 weeks of nerTMS, (b) 1 week of ST+ 2 weeks of nerTMS, (c) 2 weeks of ST+1 week of nerTMS, or (d) 3 weeks of ST (control group). This design will allow systematic evaluation of the efficacy of nerTMS and its most optimal dose for language recovery. Short- and long-term outcomes will be evaluated with aphasia testing (AT) and fMRI.

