Aim 2 (imaging): To use fMRI to assess changes in language lateralization in response to nerTMS. We will examine the relationship between the degree of pre-nerTMS language lateralization (fMRI) with the post-nerTMS language outcomes (AT) and determine whether fMRI language lateralization can predict AT performance following nerTMS targeted to the left middle cerebral artery (LMCA) stroke areas.

Aim 3 (exploratory/shaping): To explore the possible synergistic effect of constraint induced aphasia therapy (CIAT) plus nerTMS on aphasia recovery in a group of 20 LMCA stroke patients. These subjects will receive 2 weeks of nerTMS enhanced by 1 hour of daily CIAT; both therapies will be administered in open-label fashion. Patients will be evaluated with fMRI and AT as above and compared to the arm "b" of the double-blind study and to CIAT data collected in an ongoing study (R01 NS048281). This aim will gather preliminary data regarding the possible synergistic effects of nerTMS and behavioral intervention.

SIGNIFICANCE

Stroke patients tend to prioritize speaking, writing and walking as the three most important rehabilitation goals. Of note is that two of these goals involve communication. This underscores the significance of developing a successful approach to aphasia treatment for the several hundred thousand new aphasia patients each year and over 1 million stroke survivors with aphasia in the U.S. alone.

Post-stroke aphasia and its impact

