Aphasia, defined as an impaired ability to communicate, is one of the most feared symptoms of stroke. It is associated with high mortality, significant motor impairment, and severe limitations in social participation [22-26]. During the past three decades science has made great strides in developing acute treatment strategies that, in some patients, decrease or eliminate stroke-related deficits. Unfortunately, the progress in aphasia rehabilitation research has not kept pace with the development of acute therapies. Current therapy approaches are based largely on developing alternative compensatory strategies for lost functions rather than restoring them [27]. Of the ~700,000 ischemic strokes occurring annually in the United States, about 1/3 are estimated to present with aphasia as one of the symptoms; for these patients, the chances of recovery after the initial period are relatively poor [28, 29]. When substantial recovery does occur, it tends to be within the first 2 to 10 weeks. Function recovery 12 months after stroke, is thought to be very unlikely [15, 30]. Of the ~270,000 people with post-stroke aphasia only 1/3 recover sufficiently to reenter society as productive members; the majority of them develop long-term aphasia with the persistent deficits that interfere with continued productivity. Many are not able to communicate or perform activities of daily living because of this handicap and become dependent upon their families and society. These stroke victims and their families are in dire need of additional restorative therapies that will enable the stroke patients to return to society as productive members. Our preliminary data suggest that nerTMS may become one of those therapies, a finding we hope to further develop in this dosing study, which is the next logical step in advancing this field.

Repetitive transcranial magnetic stimulation (rTMS)

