If increased activation of dominant-hemisphere language circuits, stimulated by nerTMS, underlies a greater degree of improvement in language function then fMRI may be able to identify and observe these underlying changes in neural circuitry. Post-stroke neuroimaging studies that have evaluated recovery from aphasia in adults with unilateral lesions show evidence of cortical reorganization and migration of language functions to the non-dominant hemisphere after a dominant hemisphere insult [12, 13, 66]. Interestingly, one study that showed such a redistribution pattern using PET and fMRI language tasks also found negative association between increased non-dominant inferior frontal gyrus activation and recovery after an ischemic stroke [67]. The best recovery was observed in patients with peri-infarct activation on the fMRI and PET studies.

Winhuisen et al. (2007) applied inhibitory rTMS to the non-dominant language circuits and found that post-stroke aphasia recovery was dependent on the preserved left-hemispheric language centers rather than on recruitment of the non-dominant homologues [68]. Two recent studies showed that the fMRI activation may be dependent on the phase of post-stroke recovery with early right-hemispheric upregulation of the fMRI signal changes correlating with language recovery and late consolidation of the

activation in the left-hemispheric language centers [69, 70]. These and other studies support the presence of preexisting language pathways in both, the dominant and non-dominant hemispheres and suggest that in healthy conditions the circuitry in the non-dominant hemisphere is inhibited by the active circuitry in the dominant hemisphere; when the preferred pathway is interrupted (as in a stroke), the non-dominant circuitry is uninhibited, hence activated. These studies, including studies from our group, suggest that increased reliance on language circuits in the dominant hemisphere supports higher levels of recovery from aphasia after stroke [12, 13]. Navigated excitatory rTMS applied to the identified by fMRI language areas is expected to facilitate and augment the increased reliance on these areas for post-stroke aphasia recovery; language mapping with fMRI pre- and post-rTMS can be used to document its effect and to predict the likelihood of post-intervention recovery (AIM 2).

Post-stroke aphasia rehabilitation methods

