
INNOVATION

The challenge for this study is to further develop and implement nerTMS as a tool for stimulating language recovery in patients with chronic post-stroke aphasia. This challenge will be addressed by conducting a randomized, sham-controlled, dose-response trial of nerTMS in order to provide class I data from a phase III treatment trial investigating fMRI-targeted treatment for chronic post-stroke aphasia (**AIM 1**). While there is evidence that nerTMS applied to the affected hemisphere may improve post-stroke motor recovery [58] and when applied to the language-dominant hemisphere in controls may promote better language skills, nerTMS has not been tested in treatment of post-stroke aphasia or in combination with other restorative therapies (CIAT; **AIM 3**). The potential impact of this study is tremendous with the potential to improve the quality of life in hundreds of thousands of Americans. We will demonstrate that nerTMS applied to the peri-stroke regions defined by fMRI promotes language recovery, and we will determine the most efficacious and the safest dose of nerTMS (**AIM 1**). Further, while the fMRI methods developed and tested by us and others are now well established, the approach of using fMRI to localize targets for nerTMS intervention and as a way of predicting the possibility of post-stroke recovery ("point of no return"; **AIM 2**) is innovative; accomplishing this aim will establish fMRI as a clinical tool in rehabilitative medicine and allow its use for identifying intervention targets.

Figure 1 below illustrates the randomized, double-blind, sham controlled dosing trial of rTMS for the treatment of aphasia (**AIM 1**).

Figure 1. Diagram of the proposed nerTMS double-blind treatment protocol (**AIMS 1-2**) and associated testing ("AT qualitative and quantitative AT; AT – quantitative testing only).

[figure not shown]

Figure 2 below illustrates the open-label study of combined rTMS and CIAT for the treatment of aphasia (AIM 3).

[figure not shown]

Figure 2. Diagram of the proposed nerTMS+CIAT open-label treatment protocol (AIM 3) and associated testing (Abbreviations as in Figure 1)

DETAILED STUDY PROTOCOL

DAY 1 (enrollment)

Subject identified by study personnel (or referred to our team for possible study participation by clinicians in the area) will undergo screening for study participation:

The inclusion criteria are:

- Age \geq 19 years

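### Aim 2 relates baseline lateralization to the post-nerTMS aphasia score and names neither baseline score nor sham contrast; Hypothesis 2 wrongly calls a correlation evidence of efficacy

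*Combined protocol and SAP*

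**What the plan says.** Aim 2 (imaging) will "examine the relationship between the degree of pre-nerTMS language lateralization (fMRI) with the post-nerTMS language outcomes (AT". A second clause sets the target of prediction, where the team will "determine whether fMRI language lateralization can predict AT performance following nerTMS". The second clause names a level after treatment. Neither clause mentions the baseline AT score or a comparison with sham, and the combined document gives no analysis model for this aim.

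Two other places give the purpose of Aim 2 as prediction of recovery. The section on functional MRI for language localization says that mapping can be used "to predict the likelihood of post-intervention recovery (AIM 2". Innovation describes fMRI "as a way of predicting the possibility of post-stroke recovery".

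Hypothesis 2 states: "This left-hemispheric shift of language processing will correlate with behavioral response to nerTMS, representing evidence of clinical efficacy".

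The data needed for a better analysis are already planned. Aim 1 randomises four groups of 15, one of them sham only. AT and fMRI are done before treatment, within a week of the last session and three months later. The caption of Figure 1, "Diagram of the proposed nerTMS double-blind treatment protocol", carries the label for Aims 1 and 2, so the sham-controlled trial is the setting for Aim 2.

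**The concern.** Prognosis is a legitimate question, but predicting recovery means saying something beyond how severe the aphasia was at entry. A patient with mild aphasia at entry will usually score well afterwards. If LI is related to severity at entry, it will be associated with the later score with no treatment effect and no relation to change. Aim 2 could then report that LI predicts recovery when it only reflects the starting point. Without a sham contrast it also cannot say for whom nerTMS works.

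The efficacy phrase in Hypothesis 2 has a separate problem. A correlation is unchanged if every patient's AT change moves by the same amount, so it carries no information on the mean nerTMS-minus-sham difference.

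**Working it through.** The plan states no alpha, correlation, effect size or power for Aim 2, so there is no figure of its own to reproduce. From the documents: 4 × 15 = 60 randomised, of whom 3 × 15 = 45 receive some nerTMS. Everything else here is assumed: two-sided 0.05, standardised normal scores, baseline-post AT correlation 0.8 to 0.9.

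**1. Unadjusted association.** Suppose LI is unrelated to post AT once baseline AT is known. Then corr(LI, post) = corr(LI, baseline) × corr(baseline, post). Example: 0.3 × 0.8 = 0.24. By Fisher's z, atanh(0.24) × √42 = 0.245 × 6.48 = 1.59, so the chance of significance is about P(Z > 1.96 − 1.59) = 35%; simulation gives 36%. Simulated results at n=45:

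| LI-severity correlation | Implied LI-post correlation | Significant, unadjusted |
|---|---|---|
| 0 | 0 | 5% |
| 0.1 | 0.08–0.09 | 8–9% |
| 0.2 | 0.16–0.18 | 18–22% |
| 0.3 | 0.24–0.27 | 36–44% |
| 0.5 | 0.40–0.45 | 79–89% |

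With all 60 patients the row for 0.3 becomes about 46–55%.

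**2. Entry limits.** The inclusion criteria restrict the Token Test to the 40th–90th percentile. Suppose the assumed correlations hold before that restriction and the outcome is the Token Test. The baseline SD then falls from 1 to 0.42, LI-severity correlations of 0.1–0.5 fall to 0.04–0.24, and the unadjusted figure is only 5–17% (n=45).

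**3. Adjustment for baseline AT.** Under the set-up in step 1, a model with baseline AT and arm (n=60) gives about 5% throughout. Now suppose instead that LI tracks true severity and that q, the baseline-post correlation, is below 1 only because of test error. With r the correlation of LI with the observed score, the partial correlation is r(1 − q)/√[(1 − r²)(1 − q²)], which is not zero. Take an LI correlation with true severity of 0.3 and q = 0.8. Then r = 0.3 × √0.8 = 0.268, and the partial correlation is 0.268 × 0.2/√(0.928 × 0.36) = 0.093. With baseline and three arm terms, atanh(0.093) × √53 = 0.68, which gives about 10%. Over q = 0.8–0.9 the range is 8–10% at 0.3 and 15–23% at 0.5. If 0.3 and 0.5 refer to the observed score instead, the figures reach 12% and 31%.

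**4. Raw change score.** Under step 1 it leaves 7–9% at 0.3 and 11–18% at 0.5 (n=45). Under the test-error set-up in step 3 it stays at about 5%. Neither analysis is best under both set-ups.

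**5. Meaning of the pooled LI coefficient.** Suppose LI has no effect in sham and a slope of 0.2 AT SD per SD of LI in every active arm. The pooled slope averages (45/60) × 0.2 = 0.15. With a standard error of 0.085 (q = 0.8), 0.15/0.085 = 1.8, so significance is common. Simulated for slopes of 0.2–0.4, the pooled coefficient is significant in 40–90% of trials at q = 0.8 and 64–98% at 0.9. The LI-by-active interaction is detected in about 18–54% and 29–79%. A pure treatment modifier could therefore pass for prognosis.

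**6. Hypothesis 2.** With a true correlation of 0.4 between LI change and AT change and no nerTMS effect, the correlation is significant in 79% of trials (n=45) and active versus sham in 5%. With correlation 0 and a nerTMS effect of 0.8 SD of AT change, the correlation is significant in 5%. The group comparison has 0.8/√(1/45 + 1/15) = 0.8/0.298 = 2.7, or about 75% power.

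**The case against.** Aim 2 is one sentence of intent. It fixes no test, covariates or population, so a reader who infers that the plan prescribes an unadjusted correlation in treated patients goes further than the text. That stands: the 45-patient Pearson test is an illustration of the plain reading. What the text does fix is the pairing of baseline LI with a later AT level, and that pairing does not match prediction of recovery.

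Recovery may mean a level reached. The section on the impact of aphasia uses it that way when it speaks of patients who recover enough to return to society. The word is ambiguous, but even then LI is useful only if it adds to what entry severity already predicts.

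Patients are described as "in patients with chronic (>1 year) aphasia caused by a left middle cerebral artery (LMCA) stroke", and "Function recovery 12 months after stroke, is thought to be very unlikely". That makes untreated change a less likely explanation, although the eligibility list does not state the one-year limit. The baseline-severity problem does not depend on untreated recovery.

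The LI-severity correlation is unknown; at zero there is no inflation, and the entry limits may shrink it. This stands, so none of the percentages is an estimate for this trial.

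A reader might infer that Hypothesis 2 makes the correlation a criterion for trial success. Nothing says so: Hypothesis 1 and Aim 1 set out efficacy against sham separately. The fault is in the interpretation.

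**Conclusion.** The point holds. As worded, Aim 2 can attribute to LI what belongs to severity at entry, and it gives no basis for saying who benefits from nerTMS. The size depends on assumed correlations: from 5%, no inflation, to 79–89% at an LI-severity correlation of 0.5 (n=45), and only 5–17% under the Token Test entry-limit scenario.

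Two stronger conclusions are tempting and not supported. One is that baseline adjustment removes the problem. It does so only if LI is unrelated to post AT given the observed baseline score; with error in baseline AT it reduces the bias and leaves about 8–10% at 0.3 and 15–23% at 0.5. The other is that an adjusted LI coefficient pooled over arms shows pure prognosis; step 5 shows that it need not.

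The efficacy phrase in Hypothesis 2 is wrong whatever the correlations are. Aim 1's randomised comparison is unaffected. The change should be made, since it concerns what Aim 2 and Hypothesis 2 can claim.

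**What to change.** State the analyses before unblinding. Name one AT score, one post-intervention visit and one fMRI task, because the testing table lists ten tests, there are two post-intervention times, and all patients have three tasks.

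1. In all 60 randomised patients, regress post AT on baseline AT, baseline LI and arm. Report the LI coefficient as an average association with outcome given baseline, not as proof of pure prognosis. Add the association of baseline LI with AT change as a sensitivity analysis.
2. Add one pre-stated exploratory interaction of LI with active versus sham (45 v 15). Report the LI slope separately in active and sham patients, and base any statement about who benefits from nerTMS only on the interaction.
3. For Hypothesis 2, compare LI change between arms. Report the association of LI change with AT change, adjusted for arm, as mechanistic and descriptive. Delete the words that present the correlation as evidence of efficacy.

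The cost is analysis wording only; every assessment is already scheduled. The downside is power. With 15 sham patients the interaction has about 18–54% power at a baseline-post correlation of 0.8 and 29–79% at 0.9, for an assumed modification of 0.2–0.4 AT SD per SD of LI. A non-significant interaction would not show that LI is only prognostic, and claims about who benefits become more modest.

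### Hypothesis 1 expects, and exploratory Aim 3 explores, synergy of nerTMS plus CIAT, but the two comparisons named for Aim 3 cannot separate synergy from additive effects

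*Combined protocol and SAP*

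**What the plan says.** The PART Study Protocol opens with "This study will test two hypotheses". Within Hypothesis 1, "synergistic effect is expected in subjects treated with a combination of nerTMS and CIAT". Aim 3, labelled exploratory, is the only aim with combination patients. Twenty patients (OBS, in the protocol's abbreviation) receive two weeks of nerTMS with daily CIAT, and "both therapies will be administered in open-label fashion". DAY 1 (enrollment) adds that they are neither randomized nor blinded. They are to be compared with arm b "of the double-blind study and to CIAT data collected in an ongoing study (R01 NS048281"). Aim 3 ends: "This aim will gather preliminary data regarding the possible synergistic effects of nerTMS and behavioral intervention".

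Aim 1 defines the two randomized, double-blind arms that matter here as "b) 1 week of ST+ 2 weeks of nerTMS" and "d) 3 weeks of ST (control group"), with 15 patients each. ST is sham. No section names arm d as a comparator for Aim 3.

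The background section on rehabilitation methods uses the idea loosely. It speaks of therapies working in synergy, then of setting the combination against each therapy by itself, then of an incremental gain. The documents do not define synergy. For Aim 3 they give no interaction contrast, statistical model or baseline adjustment.

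**The concern.** Synergy normally means that the combination does more than the sum of the two separate effects. Showing that it beats each therapy alone is a weaker result, which purely additive effects would also produce. Aim 3 names comparators suited to the weaker question, while Hypothesis 1 and Aim 3 use the word for the stronger one. A favourable pairwise result could then be reported as support for synergy when the effects only add up, or when the open-label group gained for reasons unrelated to either therapy.

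**Working it through.** **Inputs from the documents.** OBS n = 20 (Aim 3); arms b and d n = 15 each (Aim 1); comparators are arm b and external CIAT data (Aim 3). The documents give no SD, effect size, alpha or CIAT sample size for Aim 3, so there is no figure of the plan's own to reproduce. **Assumed for illustration:** SD 1, two-sided 0.05, CIAT n = 10 to 30, independent observations.

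**Step 1: what the comparisons estimate.** Let mean change be p with neither therapy, p + a with nerTMS, p + c with CIAT, and p + a + c + i with both. Synergy is i > 0.

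- OBS − arm b = c + i
- OBS − CIAT = a + i
- OBS − arm b − CIAT = i − p
- OBS − arm b − CIAT + arm d = i

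**Step 2: identical differences, different truths.** In SD units, with p = 0:

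| nerTMS | CIAT | Both | OBS − b | OBS − CIAT | i |
|---|---|---|---|---|---|
| 0.4 | 0.4 | 0.8 | 0.40 | 0.40 | 0 |
| 0.2 | 0.2 | 0.6 | 0.40 | 0.40 | +0.2 |
| 0.6 | 0.6 | 1.0 | 0.40 | 0.40 | −0.2 |

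The two differences therefore fit additivity, synergy and sub-additivity equally well. Using all three group means does not settle it without p. With group means of 0.4, 0.4 and 0.8, i is −0.2, 0 or +0.4 when p is −0.2, 0 or +0.4.

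**Step 3: which gains mislead, and in which direction.** A practice or placebo gain shared by all groups is part of p. It cancels in both pairwise differences and makes i − p too small, so it works against a finding of synergy. A gain g confined to OBS is different: it adds g to both pairwise differences and to the four-group contrast, so arm d does not remove it. If the external CIAT patients share g, it cancels from OBS − CIAT and from the four-group contrast but stays in OBS − arm b.

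**Step 4: illustration by simulation** (1,000,000 trials per case, pooled t tests, significance counted only in favour of OBS; requiring both comparisons to be significant is a yardstick adopted here, not a rule in the protocol). The ranges span CIAT n = 10 to 30.

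- Zero interaction: both are significant with probability 0.116–0.190 at 0.5 SD per therapy, 0.381–0.545 at 0.8 SD and 0.611–0.776 at 1.0 SD.
- No effect of either therapy, 0.5 SD gain in OBS only: arm b comparison 0.296, both 0.117–0.190.
- The same gain shared by the CIAT patients: arm b comparison 0.294, both 0.017–0.019.

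**Step 5: precision of the four-group contrast.** SE = √(1/20 + 1/15 + 1/15 + 1/n), with n the CIAT sample size. This gives 0.532 for n = 10, 0.500 for n = 15 and 0.465 for n = 30. The t-based 95% half-widths are 1.07, 1.00 and 0.93 SD. DAY 1 (enrollment) requires at least three subjects per CIAT therapy group. Any correlation within those groups makes the interval wider than this.

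**The case against.** **The aim is already limited.** Aim 3 calls itself exploratory and promises preliminary data, and no section says that a favourable pairwise result will be called synergy. That stands and keeps the weight low. But the exploratory label does not make an unidentified quantity estimable, and Hypothesis 1 carries no such label.

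**Synergy may only have meant better than either therapy alone.** The background section supports that reading, and the two named comparisons address it. In that case the term in Hypothesis 1 and Aim 3 claims more than is meant, and saying so is still the remedy.

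**The missing reference group exists.** Aim 3 names two comparators but does not exclude others, and arm d is already enrolled. A reader might infer that the trial could never estimate an interaction. The documents do not support that: the gap lies in the named comparisons, not wholly in the data. Whether arm d can be used depends on CIAT data that the documents do not describe.

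**Practice gains.** A reader might infer that repeated testing would create false synergy, since the test table in DAY 2 returns to version A at NAT 3 and NAT 5. Step 3 shows the opposite direction. The background also makes spontaneous change unlikely: "Function recovery 12 months after stroke, is thought to be very unlikely".

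**The external CIAT treatment.** A reader might infer that its dose is unknown or different. CIAT PORTION says that OBS receives the protocol already implemented under R01 NS048281 and describes 45–60 minute sessions for 10 days, so a similar dose is plausible. What remains unconfirmed is the schedule, sample size and blinding behind the external data.

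**Conclusion.** The concern holds as a matter of identification, and that part rests on algebra alone, given the usual additive-scale meaning of synergy. The comparisons with arm b and with the CIAT data can speak to benefit over either therapy alone. They cannot distinguish synergy from additivity or sub-additivity.

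The risk of a falsely favourable reading has two sources: additive effects taken for synergy, and a gain specific to the open-label, non-randomized OBS group. The second also affects the weaker claim of added benefit. Arm b is blinded and includes a sham week, and the CIAT patients come from another study.

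The weight is modest: interpretation of an exploratory aim, with no decision rule attached. The simulated percentages are illustration only. Apart from the sample sizes of 20 and 15, every input to them is assumed, and they ignore correlation within therapy groups. A reader might also infer that the word synergistic must be removed throughout. That goes too far: an exploratory aim may name a possible synergy if it estimates the right contrast with caveats.

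**What to change.** 1. State in Hypothesis 1 and Aim 3 that the comparisons with arm b and the CIAT data assess combined-treatment (incremental) benefit over either therapy alone, and that synergy will not be inferred from them.
2. If patient-level CIAT data with the same instruments and timepoints are available, report OBS − arm b − CIAT + arm d on baseline-adjusted change. Present it as the exploratory estimate of synergy, with its 95% CI and no test-based claim, and allow for correlation within CIAT therapy groups.
3. Interpret every Aim 3 comparison with the caveat that OBS is open-label and non-randomized, arm b is blinded with a sham week, and the CIAT data are external. State the schedule, sample size and blinding behind those data.

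The cost is a few sentences and, if the data allow, one extra analysis; no new patients are needed. The downside is a weaker claim for Aim 3 and a wide interval for the contrast.
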